#### 8.3.3.3 EXPECTEDNESS

As defined in 8.3.4, assessment of adverse events from study data will not occur until after the participant is finished participating in the intervention. This is because all outcome data will come from secondary datasets collected at the end of the study. All adverse events that will be measured using these data (e.g., ED encounters, hospital admissions, overdose, and overdose and all-cause mortality) are expected due to the nature of opioid use disorder. Should an adverse event be reported to the researchers outside of secondary data sources, a clinician with appropriate expertise in opioid use disorder will be responsible for determining whether an adverse event (AE) is expected or unexpected. An AE will be considered unexpected if the nature, severity, or frequency of the event is not consistent with the risk information previously described for the study procedures.

#### 8.3.4 TIME PERIOD AND FREQUENCY FOR EVENT ASSESSMENT AND FOLLOW-UP

The occurrence of an adverse event (AE) or serious adverse event (SAE) for participants receiving the POINT intervention may come to the attention of recovery coaches while performing follow-up engagement. However, the study relies on administrative data to follow participants longitudinally and does not allow study personnel to assess for adverse events in real-time.

#### 8.3.5 ADVERSE EVENT REPORTING

Adverse events will be reported to the IRB and the NIDA Program Officer in regular annual reporting.

### 8.3.6 SERIOUS ADVERSE EVENT REPORTING

Serious adverse events will be reported to the IRB and NIDA Program Officer within 24 hours, and a written follow-up (including information on the date of the event, what occurred, actions taken by project staff, any planned follow up, the intervention group/study arm of the affected participant, whether the event appears to be related to the intervention) will be provided within 72 hours of the event. Confidentiality will be breached in any circumstance where mandatory reporting is required. We have put procedures in place with the social work staff at the hospital and will inform them when there are concerns of self-harm or child abuse/neglect. As this is a long-term follow-up study, we have no way of tracking a number of events that could happen.

If any adverse event is noted, we will immediately contact the IRB and inform the ED. Additionally, participant withdrawals or complaints will be monitored by [name] to ensure that study procedures have not resulted in unanticipated outcomes to participants. Results of all data safety and monitoring activities will be reported to NIDA annually. Subject withdrawals and complaints will be monitored by the PIs with assistance from the Project Manager to ensure study procedures designed to protect the privacy and confidentiality of participants are adequate and no unanticipated distress or unintended outcomes have resulted from any of the study procedures.

### 8.3.7 REPORTING EVENTS TO PARTICIPANTS

Not applicable.

### 8.3.8 EVENTS OF SPECIAL INTEREST

Not applicable.

### 8.3.9 REPORTING OF PREGNANCY

Not applicable.

## 8.4 UNANTICIPATED PROBLEMS

### 8.4.1 DEFINITION OF UNANTICIPATED PROBLEMS

Not applicable.

### 8.4.2 UNANTICIPATED PROBLEMS REPORTING

Not applicable.

### 8.4.3 REPORTING UNANTICIPATED PROBLEMS TO PARTICIPANTS

Not applicable.

## 9 STATISTICAL CONSIDERATIONS

## 9.1 STATISTICAL HYPOTHESES

Primary Endpoint:

- Overdose Admissions
  - [Measured: 1 year pre-enrollment through 1 year post-enrollment]

We hypothesize that, compared to patients in the control condition, patients receiving the POINT intervention will experience fewer subsequent admissions to the ED for overdose.

Secondary Endpoints:

- MOUD Engagement
  - [Measured: 1 year pre-enrollment through 1 year post-enrollment]
- Duration of MOUD Engagement
  - [Measured: 1 year pre-enrollment through 1 year post-enrollment]
- ED Admissions
  - [Measured: 1 year pre-enrollment through 1 year post-enrollment]
- Inpatient Hospital Admissions
  - [Measured: 1 year pre-enrollment through 1 year post-enrollment]
- Time to Relapse
  - [Measured: Enrollment through 1 year post-enrollment]
- Medicaid Enrollment for Participants Without Insurance
  - [Measured: Enrollment through 1 year post-enrollment]
- Child Welfare Involvement
  - [Measured: 3 years pre-enrollment through 1 year post-enrollment]
- Incarceration
  - [Measured: 3 years pre-enrollment through 1 year post-enrollment]

We hypothesize that, compared to patients in the control condition, patients receiving the POINT intervention will experience better recovery outcomes (i.e., higher MOUD engagement and longer duration of engagement, lower ED and inpatient admissions, longer times between relapse, higher Medicaid enrollment for those without insurance, lower child welfare involvement, and lower incarceration).

## 9.2 SAMPLE SIZE DETERMINATION

Our goal is to obtain a total of 356 patients in each study arm ( $n = 712$ ) by Month 32, which will provide us with enough patients to obtain a full year of follow-up data to detect a minimum 6% reduction in our primary outcome (subsequent overdose) at 80% power, assuming a 12% rate of subsequent overdose for the standard care arm at the 5% significance level (this is a conservative calculation based on observed subsequent overdose rates at Eskenazi and Indianapolis Emergency Medical Services).

(Note: This goal was not ultimately reached due research activities needed to stop because of the COVID-19 pandemic. Researchers developed an alternative plan to assess outcomes using a retrospective case control design that was approved by the funder. However, all planned analyses were conducted using data collected from patients who were enrolled in the trial.)

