## 4 STUDY DESIGN

### 4.1 OVERALL DESIGN

The primary objective of this pragmatic clinical trial is to replicate POINT at two new hospitals and establish POINT's effectiveness compared to standard care. In doing so, we aim to understand POINT's effect on the recovery process, including treatment and recovery outcomes and overdose. We hypothesize that POINT patients will engage in MOUD at higher rates, remain in treatment longer, and have significantly improved outcomes in comparison to the standard care group.

Hospital patients meeting the eligibility criteria at one of the two participating EDs are approached by a recovery coach or research assistant and invited to enroll in the study. Participants of the study are randomly enrolled into one of two study arms: (1) the POINT intervention arm, in which they receive ongoing recovery support services from a recovery coach or (2) the control arm, in which they receive a list of available local resources for substance use disorder from the research assistant. The study utilizes shift-level randomization, and each day of enrollment is separated into three enrollment shifts which are randomly assigned to one of the two study arms. Thus, participants' arm assignment is pre-determined by the shift in which they are discharged from the ED and enrolled into the study.

Participants are asked to complete a single structured interview at the time of their enrollment and are followed longitudinally only through administrative data, which is collected for participants from three years prior to their enrollment through two years following their enrollment.

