### 9.4 STATISTICAL ANALYSES

#### 9.4.1 GENERAL APPROACH

We will summarize patient characteristics using means and standard deviations for continuous variables and counts and proportions for categorical variables. Initial analysis of outcomes (using data pulled at 9 months) will focus on MOUD engagement one-month post overdose, as all other outcomes will be too distal to observe any meaningful change. This time period is based on our prior POINT experience demonstrating initial engagement tends to happen within 1-2 weeks of overdose. We will focus on immediate outcomes (e.g., treatment engagement, length, dropout). While observed change in more distal outcomes (e.g., subsequent overdose and mortality) is unlikely to be seen in such a short pilot period, we will look at them and, if needed, adjust the benchmark (established based on our experience at Eskenazi) for the power analysis. Summary of outcome measures will be computed similarly. The 95% confidence intervals of outcome measures for the POINT and standard care arms will be used to estimate the rate of binary outcomes and mean of continuous outcomes.

The primary analysis involves comparison of outcome measures post ED discharge between the POINT and standard care arms. Binary outcome measures (e.g., MOUD engagement and dropout, subsequent overdose, overdose mortality, and all-cause mortality) will be compared between the POINT and standard care arms using the Fisher's exact test. Length of MOUD treatment will be compared using the Wilcoxon rank sum test. Comparison of the length of time to relapse will be conducted using the survival analysis. Time to relapse will be plotted using the Kaplan Meier curve and comparison between the POINT and standard care arms will be performed using the log rank test.

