#### 9.4.2 ANALYSIS OF THE PRIMARY ENDPOINT(S)

Questions	Defined/explained
Primary endpoint	
Describe how the primary endpoint is calculated, if not readily apparent	Change in Overdose Admissions: Using electronic health records, it is calculated as the total combined number of overdoses resulting in an emergency department presentation within the specified time period.
Describe the scale (nominal/binary/categorical, ordinal, interval); state if it is measured as a single endpoint/summary measure or repeated measure	binary
Describe the statistical procedure(s) that will be used to analyze the primary endpoint (e.g., multiple regression, repeated measures mixed models, logistic regression, Analysis of Covariance (ANCOVA)). Describe the covariates and factors in the model. Provide a rationale for covariates and how they will be selected to achieve a parsimonious model. If the decision to specify covariates is deferred for the SAP, indicate here.	Summarized using frequencies and percentages and then compare arms using the Fisher's exact test.
Describe how results of statistical procedure(s) will be presented (e.g., adjusted means (Least-squares means (LSMEANS)) with standard errors, odds ratios with 95% confidence intervals, prevalence rates, number-needed-to-treat)	Presented using frequencies and percentages
Describe details to check assumptions required for certain types of analyses (e.g., proportional hazards, transformations or, when appropriate, nonparametric tests)	The nonparametric Fisher's exact test is used to compare the primary endpoint.
Describe the Populations for which the analysis will be conducted, as discussed in Section 9.3, Populations for Analyses	All study participants
Describe how missing data will be handled (e.g., type of imputation technique, if any, and provide justification), and approach to handling outliers, non-adherence and lost to follow-up	We do not expect there to be a large amount of missing data due to the use of administrative datasets. However, missing values may occur when subjects die during the specified time period. Sensitivity analysis is performed by excluding subjects who die during the specified time period.

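### Section 9.2 claims 80% power at 356 per arm, but the planned Fisher's exact test, read as two-sided, has 77.1% there and needs 380 per arm for 80%

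*Combined protocol and SAP*

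**What the plan says.** Section 9.2 plans 356 patients per arm (712 in total) to "detect a minimum 6% reduction in our primary outcome (subsequent overdose) at 80% power, assuming a 12% rate of subsequent overdose" under standard care, at a 5% significance level. It does not say which test the power refers to, or whether the test is one- or two-sided. A note in the same section adds: "This goal was not ultimately reached due research activities needed to stop because of the COVID-19 pandemic". The number actually enrolled is not given.

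The test is named elsewhere. Section 9.4.1 says that binary outcomes, subsequent overdose among them, "will be compared between the POINT and standard care arms using the Fisher's exact test". Section 9.4.2 says of the primary endpoint: "Summarized using frequencies and percentages and then compare arms using the Fisher's exact test". Neither section states sidedness. The hypothesis in section 9.1 is directional: "patients receiving the POINT intervention will experience fewer subsequent admissions to the ED for overdose".

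On reporting, section 9.4.1 plans intervals arm by arm ("The 95% confidence intervals of outcome measures for the POINT and standard care arms will be used to estimate the rate of binary outcomes"), and section 9.4.2 says the primary result is "Presented using frequencies and percentages". Section 4.1 states: "The study utilizes shift-level randomization".

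**The concern.** Power belongs to a particular test. A power figure from the uncorrected chi-square approximation does not carry over to Fisher's exact test, which is conservative at these event rates and so has less power at the same sample size. Section 9.2 also calls its calculation conservative, while for the planned test read as two-sided the power claim errs on the optimistic side.

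A reader of 9.2 takes the type II error at full enrollment to be 20%. If it is higher, a non-significant result excludes less than the reader believes. That matters more here because enrollment fell short, so actual power is lower still, and no between-arm interval is planned that would show the precision achieved.

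**Working it through.** **Inputs.** From section 9.2: control rate 12%, 6% reduction, α = 0.05, power 80%, 356 per arm, equal arms. From 9.4.1 and 9.4.2: Fisher's exact test on a binary endpoint. The reduction must be absolute (12% to 6%), since a relative 6% reduction (12% to 11.28%) would need 31,144 per arm by the same formula. Patients are treated as independent throughout.

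**Step 1: reproduce 356.** The two-sided pooled formula without continuity correction is

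n = [z₀.₉₇₅ √(2p̄(1−p̄)) + z₀.₈₀ √(p₁(1−p₁) + p₂(1−p₂))]² / (p₁−p₂)²

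With p₁ = 0.12, p₂ = 0.06, p̄ = 0.09:

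- √(2 × 0.09 × 0.91) = 0.4047
- √(0.12 × 0.88 + 0.06 × 0.94) = √0.1620 = 0.4025
- n = (1.960 × 0.4047 + 0.8416 × 0.4025)² / 0.0036 = 355.94 (computed without rounding), so 356.

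The plan's figure is therefore reproduced. Other standard formulas do not give it:

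| Formula | Two-sided n per arm | One-sided n per arm |
|---|---|---|
| Pooled | 355.94 | 280.26 |
| Unpooled | 353.20 | 278.22 |
| Average variance | 357.12 | 281.31 |
| Arcsine | 347.47 | 273.70 |
| Pooled, continuity-corrected | 388.56 | 312.70 |
| Unpooled, continuity-corrected | 385.81 | 310.65 |

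Only the two-sided pooled form rounds up to 356. This is the ground for reading the plan as two-sided.

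**Step 2: power of the planned test.** For every pair of event counts, take the product of the two binomial probabilities and sum it over the pairs that the test rejects at p ≤ 0.05. The two-sided Fisher p-value sums all tables no more probable than the observed one.

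| Test, 12% vs 6% | n per arm | Exact power |
|---|---|---|
| Chi-square, uncorrected, two-sided | 356 | 80.7% |
| Fisher, two-sided | 356 | 77.1% |
| Fisher, two-sided | 379 | 79.97% |
| Fisher, two-sided | 380 | 80.09% |
| Fisher, one-sided 5% | 356 | 85.5% |
| Fisher, one-sided 5% | 305 | 80.03% |

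- No n from 340 to 379 reaches 80% with two-sided Fisher, and none from 380 to 430 falls below it.
- Defining the two-sided p-value by doubling the one-sided one gives the same 77.1% and 380.
- Shortfall: 80 − 77.1 = 2.9 points; 380 − 356 = 24 per arm, 48 in total.
- The choice of sidedness moves the power of the planned test by 85.5 − 77.1 = 8.4 points.
- Actual type I error at a common rate of 12% and 356 per arm: Fisher two-sided 3.8%, chi-square 5.0%.

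**Step 3: sensitivity to the assumed rate.** Holding the 6-point difference, two-sided Fisher power at 356 per arm is 72.8% for 13% vs 7% and 81.6% for 11% vs 5%.

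**Step 4: precision at full enrollment.** Wald half-width for the difference: 1.96 × √(0.1620/356) = 0.0418. An observed 6-point difference would carry a 95% interval of about 1.8 to 10.2 points. With fewer patients the interval is wider.

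**Step 5: illustration of the missed target.** The enrolled numbers below are assumptions, since the documents give none. Two-sided Fisher power for 12% vs 6% would be 69% at 300 per arm, 60% at 250 and 49% at 200.

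**The case against.** The case for leaving 9.2 alone has four parts.

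- **356 is not a miscalculation.** This stands. It is correct for the uncorrected chi-square test. The defect is that the plan sizes for one test and analyzes with another.
- **The gap is small beside the uncertainty in the inputs.** Also true. If the POINT-arm rate were 5.8% rather than 6.0%, two-sided Fisher power at 356 would be 80.4%. That limits the weight of the point, but it does not make 80% the right figure for the rates that 9.2 itself states.
- **Sidedness is inferred, and a one-sided 5% Fisher test has 85.5% power, so the shortfall would vanish.** The inference rests on 356 fitting only a two-sided formula, while the hypothesis in 9.1 is directional. The sponsor should confirm it. On either reading, 80% is not the power of the planned test at 356.
- **The target was missed, so the figure describes a trial that never happened.** The document does say so openly. Correcting the figure changes no design decision, but the stated power of the planned design remains wrong, and the shortfall makes the actual numbers and a between-arm interval more useful to the reader.

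The enrolled number and the interval are reporting additions. The conclusion about power does not depend on them.

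**Conclusion.** The concern holds. At 12% vs 6% and 356 per arm, two-sided Fisher's exact test at 5% has 77.1% power, so the type II error is 22.9% rather than 20%; 80% needs 380 per arm. This assumes a two-sided test (inferred), an absolute 6-point reduction and independent patients. The size is modest and the error is in the safe direction for type I error.

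Two further losses cannot be quantified from the documents: shift-level randomization (no intraclass correlation or number of patients per shift is given) and the missed enrollment target (no enrolled number is given). The point should be corrected, but it does not call for a different test or a larger trial.

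**What to change.** Once the sponsor has confirmed that the test is two-sided, restate section 9.2 along these lines: *With 356 per arm, a two-sided Fisher's exact test at the 5% level has about 77% power to detect an absolute reduction from 12% to 6%, before any allowance for shift-level randomization.* If the test was meant to be one-sided at 5%, say so and give 85.5% instead.

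Add the number enrolled in each arm, and plan a 95% confidence interval for the between-arm difference in the primary outcome. State whether that interval treats patients as independent or accounts for shifts. Keep Fisher's exact test and add no patients.

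The cost is one sentence in 9.2, one count per arm and one interval from data already held. The only downside is a slightly less favorable power statement.

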### 9.3 POPULATIONS FOR ANALYSES

All participants consented to the trial will be included in the analyses.

### 9.4 STATISTICAL ANALYSES

#### 9.4.1 GENERAL APPROACH

We will summarize patient characteristics using means and standard deviations for continuous variables and counts and proportions for categorical variables. Initial analysis of outcomes (using data pulled at 9 months) will focus on MOUD engagement one-month post overdose, as all other outcomes will be too distal to observe any meaningful change. This time period is based on our prior POINT experience demonstrating initial engagement tends to happen within 1-2 weeks of overdose. We will focus on immediate outcomes (e.g., treatment engagement, length, dropout). While observed change in more distal outcomes (e.g., subsequent overdose and mortality) is unlikely to be seen in such a short pilot period, we will look at them and, if needed, adjust the benchmark (established based on our experience at Eskenazi) for the power analysis. Summary of outcome measures will be computed similarly. The 95% confidence intervals of outcome measures for the POINT and standard care arms will be used to estimate the rate of binary outcomes and mean of continuous outcomes.

The primary analysis involves comparison of outcome measures post ED discharge between the POINT and standard care arms. Binary outcome measures (e.g., MOUD engagement and dropout, subsequent overdose, overdose mortality, and all-cause mortality) will be compared between the POINT and standard care arms using the Fisher's exact test. Length of MOUD treatment will be compared using the Wilcoxon rank sum test. Comparison of the length of time to relapse will be conducted using the survival analysis. Time to relapse will be plotted using the Kaplan Meier curve and comparison between the POINT and standard care arms will be performed using the log rank test.

The secondary analysis involves comparing outcome measures pre- and post-ED discharge for POINT patients. Binary outcomes including child welfare involvement will be compared using the McNemar's test and the continuous outcome including the days of incarceration will be compared using the Wilcoxon signed rank test due to the skewness of the data. Additional analyses will be conducted to account for patient characteristics in the comparison between the POINT and standard care arms using logistic regression for binary outcomes, Poisson regression for length of MOUD treatment, and Cox proportional hazards model for time to relapse. For the comparison pre- and post-ED discharge in the POINT arm, generalized estimating equations approach will be performed using logistic regression for Medicaid enrollment and child welfare involvement and Poisson regression for days of incarceration. Hospitals will be included in the models as a fixed effect to account for the potential differences in patient population across hospitals.

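### The pre/post analysis of Medicaid, child welfare and incarceration uses the POINT arm alone, so change shared with controls can be read as a POINT effect

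*Combined protocol and SAP*

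**What the plan says.** Section 9.4.1 defines a secondary analysis and limits it to one arm twice. The tests come first: "The secondary analysis involves comparing outcome measures pre- and post-ED discharge for POINT patients". For these patients, "Binary outcomes including child welfare involvement will be compared using the McNemar's test"; days in custody get a Wilcoxon signed rank test. The models follow: "For the comparison pre- and post-ED discharge in the POINT arm, generalized estimating equations approach will be performed", with logistic regression for Medicaid and child welfare and Poisson regression for incarceration days.

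Section 9.1 frames the same endpoints against control: "compared to patients in the control condition, patients receiving the POINT intervention will experience better recovery outcomes". It lists "Medicaid Enrollment for Participants Without Insurance" with a window that starts at enrollment. Child welfare and incarceration run from 3 years before enrollment to 1 year after.

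Section 4.1 describes the administrative data, "which is collected for participants from three years prior to their enrollment through two years following their enrollment", and Section 8.1 confirms that they are obtained for each participant. Control-arm histories are therefore available.

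Between-arm tests are also planned. Section 9.4.1 makes the post-discharge comparison of arms the primary analysis. Section 9.4.3 classes Medicaid and child welfare as binary and incarceration as interval, and assigns Fisher's exact test to binary variables and the rank sum test to continuous ones.

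**The concern.** Everyone enters at an overdose or another opioid-related ED visit (Section 5.1). Section 4.3 regards that visit as a moment of raised readiness for treatment, which would apply in either arm. The period after it is always later in calendar time, in a study whose enrollment was interrupted by the pandemic. Deaths also shorten it. None of these influences is specific to POINT, and a before/after test in one arm cannot separate them from the intervention.

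Section 3 words the objectives as assessments of POINT's effectiveness. A significant improvement within POINT could be reported under that wording although controls changed just as much. The randomised control arm that would show this is not used in this analysis.

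**Working it through.** **1. The plan's own figure.** The documents give none for the pre/post analysis. The only design figure is 356 per arm for the between-arm primary endpoint (Section 9.2: 12% against 6%, 5% level, 80% power). With a two-sided test and pooled variance:

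n = [1.96 × √(2 × 0.09 × 0.91) + 0.8416 × √(0.12 × 0.88 + 0.06 × 0.94)]² / 0.06² = (0.7932 + 0.3388)² / 0.0036 ≈ 356.

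It reproduces, but it says nothing about this analysis. Below, 356 is the upper end of a range of arm sizes. Planned enrollment was not met and the number enrolled is not given, so 100 per arm is shown as an assumed lower value.

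**2. Effect of the stated windows (Section 9.1: 3 years before, 1 year after).** Assume a constant process and no POINT effect.

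- *Incarceration days.* The expected post/pre ratio without an offset is 1/3 ≈ 0.33. Simulation gave 0.33 to 0.34 (500 runs; assumed 40% at risk, 0.5 spells per year, mean spell 60 days). The POINT-only signed rank test was significant in 100% of runs at 356 and 91% at 100. With 1-year windows on both sides the rates were 6.2% and 6.4%.
- *Child welfare, any involvement.* With annual risk p, the pre probability is 1 − (1 − p)³ and the post probability is p. All risks are assumed.

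| Annual risk | Pre (3 y) | Post (1 y) | POINT-only McNemar significant, n = 356 | n = 100 |
|---|---|---|---|---|
| 3% | 8.7% | 3% | 93% | 32% |
| 5% | 14.3% | 5% | 99.7% | 59% |
| 10% | 27.1% | 10% | 100% | 90% |

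A between-arm comparison of change was significant in about 5% of runs in all these cases.

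**3. Shared background change with equal windows.** Assume a 30% pre rate, within-person latent correlation 0.3, the same relative fall in both arms and no POINT effect (1,500 runs).

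| Shared fall | POINT-only, n = 356 | POINT-only, n = 100 | Between-arm change, both sizes |
|---|---|---|---|
| 0% | 4.5% | 3.5% | about 5% |
| 10% | 13% | 6% | about 5% |
| 20% | 48% | 13% | about 4–5% |
| 30% | 84% | 29% | about 5% |
| 40% | 98% | 49% | about 5% |

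Equalising the windows removes the artefact in step 2 but not this one.

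**4. Medicaid.** The plan states that a "generalized estimating equations approach will be performed using logistic regression for Medicaid enrollment and child welfare involvement", but Section 9.1 defines no pre-enrollment window. Suppose pre-status is taken at enrollment in the uninsured subset. It is then 0 for everyone, and discordant pairs can run one way only. The exact McNemar p-value with b new enrollments is 2 × 0.5^b:

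- b = 5: 0.0625
- b = 6: 0.031

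The number of uninsured participants does not enter. With an assumed 50 uninsured POINT participants, the chance of at least six enrollments is 38%, 95% or 99.9% if 10%, 20% or 30% would enroll without POINT. In the GEE logistic model the pre cell has no events, so the odds ratio is not estimable.

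**The case against.** The strongest reply is that the controlled answer is already in the plan. Section 9.4.1 puts the between-arm comparison first, and Section 9.4.3 assigns tests by variable type, which reaches all three endpoints. The adjusted between-arm logistic regression in Section 9.4.1 also reaches the binary ones. This stands. A reader might infer that these endpoints have no randomised comparison at all, and the documents do not support that. What remains is that the only test or model naming any of the three is the uncontrolled one, with no limit on its interpretation. Section 9.4.3 adds that each endpoint is analysed once, so the named test may be taken as the analysis.

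Second, a pre/post test that rejects because outcomes changed is correct for its own null hypothesis. It misleads only if read causally, and no section states that reading outright. This also stands, and it is why a descriptive label would settle much of the matter.

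Third, the crisis-peak argument fits overdose and ED use better than child welfare or jail days. An overdose could itself prompt a child welfare case, which would work against POINT. A reader might infer that improvement without intervention is to be expected here, but the documents give neither direction nor size. They also do not show what share of post windows reached the pandemic.

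Fourth, the Medicaid result is conditional. Someone uninsured at enrollment may have had Medicaid earlier, so what is documented is an undefined pre-period, not a proven empty cell. McNemar's test reaches Medicaid only through the general reference to binary outcomes; GEE is the method named for it. Nor is lack of insurance an enrollment criterion: Section 5.1 has none, and it only defines the subset for this endpoint.

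Finally, this is a secondary analysis, and Section 3 lists child welfare and incarceration as exploratory. That limits the stakes.

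**Conclusion.** The point holds: the pre/post analysis is uncontrolled, its hypotheses are comparative, and control data for the same periods are collected. The plan should be changed, but the primary endpoint's between-arm inference is not affected.

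The firmest part is the window mismatch, which rests on the plan's own 3-year and 1-year windows. Unless these are equalised or offset, a constant process appears as a fall of about two thirds in incarceration days. The rates for shared background change (13% to 98% at 356 per arm and 6% to 49% at 100, for falls of 10% to 40%) illustrate sensitivity under assumed inputs. They do not estimate what happened in this trial. The Medicaid figures hold only if pre-status is taken at enrollment.

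A reader might go further and conclude that a POINT-only improvement must be spurious, or that the Medicaid comparison is certain to fail. The documents establish neither.

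**What to change.** In Section 9.4.1:

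- Fit the GEE models for child welfare and incarceration days in both arms, with arm, period and arm-by-period, and take the interaction as the POINT effect.
- Use equal-length windows before and after enrollment, or an exposure offset. The offset suits the Poisson model for days directly; for the logistic model equal windows are simpler.
- Report POINT-only pre/post change as descriptive, without a p-value.
- Remove Medicaid from the pre/post analysis. State explicitly the between-arm comparison of post-enrollment Medicaid among those uninsured at enrollment.

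The cost is SAP wording and a few lines of code; no new data are needed. The interaction has a wider interval than the uncontrolled change. With equal arms and similar variance of change, its standard error is about √2 ≈ 1.4 times as large.
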